Low Dose Ketamine Infusion for Analgesia in the Emergency Department to Reduce Side Effects

Study Protocol and Analysis Plan

NCT05518877

June 6, 2024

Study Title: Low Dose Ketamine Infusion for Analgesia in the ED to Reduce Side Effects: A Double Blind, Double Dummy Randomized Controlled Trial

Principle Investigator: PI: [name], DO
Sub-Investigator: Sub-I: [name]

Address: Summa Health Department of Emergency Medicine
[name]
[name]

1. Purpose of Study

Research has shown low dose ketamine (LDK) Intravenous push (IVP) (0.3mg/kg) to have equivalent pain reduction in moderate to severe acute pain in the Emergency Department (ED) when compared to standard of care of morphine IVP (0.1mg/kg). Ketamine has been shown to produce side effects in these studies, including dizziness, feeling of unreality and mood changes. There were no unexpected side effects or adverse events during this trial.¹ Another study compared IVP with a slower infusion of LDK and showed a decrease in side effects while maintaining similar analgesic efficacy. This trial found increased feelings of unreality for the IVP group (difference of 37.5%) as well as increased rates of sedation.²

In clinical practice, increasing the time/duration of the infusion has resulted in a decrease of reported side effects from patients while still maintaining analgesia. There have been no studies done to prove that there is a further reduction in side effects with a longer LDK infusion. We believe that increasing the infusion time to greater than 15 minutes will reduce the frequency and intensity of expected side effects of ketamine felt by recipients and allow for further use of ketamine as a non-opiate analgesic in the ED.

Overall aims of project:

1. Reduce overall incidence and severity of known side effects of low dose ketamine when given over 30 minutes versus 15 minutes.
2. Maintain adequate pain control, as determined by a Visual Analogue Score (VAS) of ≤ 5 cm (50mm) at 30 minutes after start of ketamine infusion.

Hypothesis: Slow infusion of LDK over 30 minutes will provide adequate pain control (as defined by VAS score of ≤ 5 cm (50mm)), and reduce incidence and severity (by at least 20% or 1 point on Side Effects Rating Scale for Dissociative Anesthetics [SERSDA] scale) of known side effects when compared to LDK given over 15 minutes in moderate to severe acute pain for patients presenting to the ED.

2. Background and Rationale

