use seems to be due to the side effect profile that is bothersome to some patients. A previous study already showed improvement in side effects, mainly dizziness, when given over a longer period of time (15 minutes). We are hypothesizing that further increasing the administration duration will produce even less side effects while maintaining analgesic properties.

Literature reviews have been done that elaborate on the common side effects of ketamine when given for analgesia. One noted most common events to be nausea, altered mood, psychomimetic effects and headaches when given intravenously for complex regional pain.¹² Another article noted that there seemed to be psychomimetic effects along with hypertension when given for pain control via intravenous infusion, although appeared to improve after infusion was complete.¹³ Similar side effect profile in terms of psychomimetic effects has been seen in other studies and include dizziness, blurred vision, vertigo, nausea/vomiting, dysphasia, nystagmus, nightmares or vivid dreams, impaired motor function and memory deficit but like other studies, improves rapidly after infusion is complete. Cardiovascular effects secondary to the catecholamine release after administration have also been documented. The main effects appear to be tachycardia, hypertension and increase in cardiac output and recommend use of cardiac monitoring but do not seem to be long lasting effects.¹⁴

This study has been determined to be exempt from FDA IND requirements based on all criteria for exemption being met.

3. Study Design

The location of this study will be the Akron City Hospital Emergency Department. The trial will enroll approximately 48 evaluable subjects. An evaluable subject is defined as a subject who completes the entire infusion (30 minutes) and provides a 30 minute VAS and SERSDA score.

This will be an intent to treat prospective, double blind, double-dummy, randomized trial. The primary outcome will be a comparison of side effects of sub dissociative dose ketamine given by slow IV infusion over 15 minutes vs 30 minutes in treatment of moderate to severe acute pain in ED patients. The secondary outcome will be adequate pain control (VAS ≤ 5 cm(50mm)) and need for rescue analgesia between the two groups.

The control group will receive slow IV infusion of ketamine over 15 minutes. The experimental group will receive slow IV infusion of ketamine over 30 minutes.

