If the patient meets all eligibility criteria, they will be consented by study staff members and then randomized to receive ketamine 0.25mg/kg in 100cc normal saline (NS), up to a

maximum of 30mg total dose, as an IV infusion over the specified time, as well as “placebo” 100cc NS over the other time slot.

[figure not shown]
If during the baseline assessment, immediately prior to the start of infusion, the subject reports an improved pain score (VAS < 5 cm(50mm)), the subject will be considered no longer eligible. The infusion will not be administered, and the subject will be removed from the study.

Since the subject was randomized, the group allocation (control or experimental group) for that subject will be reassigned to the randomization block to maintain a total of 48 enrolled (infused) subjects.

Pharmacy staff will provide the study medication in a blinded fashion to the nurse who will use infusion pumps to deliver both study medication and placebo simultaneously. Nursing staff will receive training on administration of the study medication prior to starting the study.

We will measure the side effect profile using the Side Effects Rating Scale for Dissociative Anesthetics (SERSDA) along with the Visual Analog Scale (VAS) (Appendix A).

Visual Analogue Scale scoring is done by asking the subject to mark the spot on the VAS Pain Assessment Tool (0-10cm) to indicate their perception of pain. Following this, the investigator scores the intensity of pain according to the 0-100mm corresponding scale (one instrument i.e., 5cm= 50mm). The VAS is a validated, subjective measure for acute and chronic pain. See below for exact tool that will be used.

Vital signs (heart rate, blood pressure, respiratory rate, and oxygen saturation) will also be obtained at 0, 5, 15, 30, 60, and 90 minutes from the start of the ketamine/NS placebo infusion.

Ketamine 30 min vs 15 min

Version: 7

Date: 06.06.2024

Page 7 of 15

Rescue Medication

At 30, 60 or 90 minutes post start of the ketamine infusion, if the study subject has a VAS score that is between 5-10cm (50-100mm), a **single** dose of both acetaminophen 1,000mg (oral) and ketorolac (15-30mg IV) will be given. If alternative medications are required, the study investigator will be consulted.

NOTE: EPIC recommends a ketorolac dose of 15mg IV if subject weight is less than 50kg or subject age is ≥ 65 years.

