3.1 Subject Population

Inclusion and Exclusion Criteria

Ketamine 30 min vs 15 min

Version: 7

Date: 06.06.2024

Page 8 of 15

Inclusion criteria:

- Patients 18 years of age or older
- Primary complaint of acute moderate to severe pain on VAS/numeric pain scale (a score of ≥ 5 cm which corresponds to 50mm).
- Pain described as abdominal, flank, back, musculoskeletal, or traumatic chest pain
- Must be alert and oriented times three
- Able to provide informed consent.

Exclusion criteria:

- Pregnant
- Breastfeeding
- Altered mental status
- Known or reported allergy, hypersensitivity, or intolerance to ketamine
- Unstable vital signs (systolic blood pressure < 80 or > 180 mmHg, heart rate < 50 or > 150 beats per minute, and respiratory rate < 10 or > 30 breaths per minute)
- History of unstable heart disease, such as arrhythmias, congestive heart failure, or coronary heart disease.
- History of untreated or uncontrolled thyroid disease
- Acute head or eye injury
- Active or current abuse of alcohol or illicit drugs
- Known intracranial hypertension
- Hepatic or renal insufficiency
- Current active manic phase of bipolar disorder
- Active delusions, hallucinations, or schizophrenia
- Patients who have recent fentanyl use within 60 minutes or other analgesic use (opiates) within 4 hours of study enrollment (signing of consent)
- Patients who have enrolled in the study during a previous ED encounter
- Chronic use of opiates (i.e.: fentanyl patch, SR opiates)

It will be at the discretion of the treating ED physician who is taking care of the patient to determine whether the patient is appropriate for the study. If it is determined the patient requires a more urgent form of pain control intervention, the patient will be excluded.

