3.3 Outcomes/Objectives

The primary objective of this study is to attempt to prove that increasing the length of ketamine administration decreases overall incidence and severity of side effects. The side effects to be monitored include fatigue, dizziness, headache, feeling of unreality, hearing, vision, or mood changes, generalized discomfort, and hallucinations. Our goal is to have at least a 20% decrease in overall scores, which equals to a “1” point decrease on the SERSDA scale. SERSDA measures severity of nine adverse effects based on a 5-point scale from “0” (no adverse effect) to “4” (very bothersome effect).

The primary outcome measure of this study is the reduction of the overall side effects as measured by the Side Effect Rating Scale for Dissociative Anesthetics (SERSDA) at 30 minutes.

The secondary objective is to ensure that adequate pain control (VAS ≤ 5 cm) is maintained when ketamine administration is prolonged. To do this we will be measuring pain scores on the 100mm VAS at each protocol specified interval (0, 5, 15, 30, 60 and 90 minutes from the infusion start time, which is defined as time zero). Studies have shown that for clinical significance in pain reduction, there needs to be at least a 13mm difference on the 100mm VAS pain scale.¹⁵

Ketamine 30 min vs 15 min

Version: 7

Date: 06.06.2024

Page 10 of 15

The secondary outcome measure is the severity of self-reported pain on the standard 100mm VAS pain scale (0-100) at 30 minutes.

The need to administer rescue analgesic medication will also be assessed, starting at 30 minutes and again at 60 and 90 minutes post start of the infusion (Time 0).

We will also be monitoring the need for the administration of other interventions to treat ketamine side effects (nausea etc.), as well as vital signs.

The Richmond Agitation Sedation Scale (RASS) (Appendix A) will be used to collect additional data.

Study Schedule

	Time 0 min	Time 5 min	Time 15 min	Time 30 min	Time 60 min	Time 90 min
VITAL SIGNS	X	X	X	X	X	X
SERDSA		X	X	X	X	X
VAS	X	X	X	X	X	X
RASS		X		X		X

4. Data Analysis/Plan

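### Sections 3 and 3.3 name different secondary outcomes; the binary one has no stated test and is likelier to miss a real loss of pain control

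*Combined protocol and SAP*

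**What the plan says.** Section 3 (Study Design) gives a binary outcome with two components and no time point in the sentence: "The secondary outcome will be adequate pain control (VAS ≤ 5 cm(50mm)) and need for rescue analgesia between the two groups".

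Section 3.3 gives a continuous outcome at one time point: "The secondary outcome measure is the severity of self-reported pain on the standard 100mm VAS pain scale (0-100) at 30 minutes". The same section states its objective on the threshold: "The secondary objective is to ensure that adequate pain control (VAS ≤ 5 cm) is maintained when ketamine administration is prolonged". It then adds rescue as a further item: "The need to administer rescue analgesic medication will also be assessed, starting at 30 minutes". Section 3.3 therefore contains all three elements but calls only continuous VAS the secondary outcome measure.

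Aim 2 in section 1 fixes the time of the threshold: "Visual Analogue Score (VAS) of ≤ 5 cm (50mm) at 30 minutes after start of ketamine infusion". The hypothesis in section 1 uses the same cut-off.

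For interpretation, section 3.3 cites a clinical standard in millimetres: "there needs to be at least a 13mm difference on the 100mm VAS pain scale".

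Section 4 assigns a mixed model to continuous outcomes. It names Fisher's exact and Pearson chi-square tests for adverse event rates only. It gives no test for adequate control or rescue, no margin for what counts as maintained control, and no VAS mean or SD.

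The 50 mm boundary appears in two further rules. Rescue applies "if the study subject has a VAS score that is between 5-10cm (50-100mm") at 30, 60 or 90 minutes. Entry requires "a score of ≥ 5 cm which corresponds to 50mm".

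**The concern.** Keeping pain control is half of the trial's hypothesis. Two definitions of the outcome that tests it leave open which one decides the matter, and the choice could be made after the data are seen. The two are not equally sensitive. Cutting a 0–100 mm score at 50 mm discards information and takes no account of where each patient started. If slower infusion did weaken analgesia, the binary version would be the more likely to report no difference.

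The boundary causes a smaller problem inside the section 3 outcome. A patient who scores exactly 50 mm at 30 minutes counts as a success on one component and a rescue case on the other.

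**Working it through.** **1. The plan's own figure.** Section 4 gives 24 per arm for a SERSDA difference of 1 unit, SD 1.2, 80% power, two-sided 5%. The normal approximation is n = 2 × (1.960 + 0.842)² × 1.2² / 1² = 22.6, so 23 per arm. The t-test version gives 23.6, so 24 per arm, with power 80.7%. The stated 48 reproduces, but it is sized on side effects and says nothing about VAS.

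**2. Assumptions for VAS.** I took SD 20, 25 or 30 mm; 30-minute mean in the better arm 35, 45, 50 or 55 mm; and a true difference of 0 or 13 mm. Scores were normal and cut to 0–100 mm. There were 20,000 simulated trials per setting with 24 per arm, all tests two-sided at 5%. A t-test on 30-minute VAS was compared with Fisher's exact test, and with uncorrected Pearson chi-square, on VAS ≤ 50 mm.

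**3. One setting by hand.** Take means 45 and 58 mm, SD 25.
- Continuous: SE = 25 × √(2/24) = 7.22 mm and 13/7.22 = 1.80, which gives power of about 42%.
- Binary: the shares at or below 50 mm are Φ((50 − 45)/25) = Φ(0.20) = 0.58 and Φ((50 − 58)/25) = Φ(−0.32) = 0.37. Simulated power is about 23% by Fisher and 32% by chi-square.
- The t-test and Fisher differ on significance in 24% of trials.

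**4. True difference of 13 mm, range over the four means.**

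| SD (mm) | Power, t-test | Power, Fisher | Power, chi-square | t-test and Fisher differ | t-test and chi-square differ |
|---|---|---|---|---|---|
| 20 | 60% | 28–34% | 39–46% | 29–35% | 23–28% |
| 25 | 41–42% | 19–23% | 28–32% | 24–26% | 20–22% |
| 30 | 31% | 14–16% | 22–24% | 18–20% | 16–18% |

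**5. Direction of the disagreement at 13 mm.** The t-test alone is significant in 17–33% of trials, and Fisher alone in about 2%. In the step 3 setting the figures are 21.5% and 2.3%, so 21.5/(21.5 + 2.3) = 90% of disagreements are the binary test missing the difference.

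**6. No true difference.** The t-test and Fisher differ in 4.5–5.3% of trials, and the t-test and chi-square in 5–7%. Both tests are usually non-significant.

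**7. Precision of the continuous version.** The unadjusted 95% CI half-width is 2.013 × SD × √(2/24), which is 11.6, 14.5 and 17.4 mm for SD 20, 25 and 30.

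**8. The 50 mm boundary.** Section 3 removes a patient before infusion only if VAS is below 5 cm, so a patient at exactly 50 mm is treated. If the score is still 50 mm at 30 minutes, that patient meets the definition of adequate control and also falls in the rescue range.

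**The case against.** A reader might infer that the two definitions will often give different verdicts, or even contradictory ones. The documents do not support that. The plan expects equal analgesia, and then the two differ in only about 1 trial in 20. Where the arms do differ, the disagreement is lost power, not opposite conclusions.

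A reader might also infer a materially inflated false-positive rate from choosing between versions. That rate reaches about 8% only if the t-test, Fisher and chi-square are all tried; the t-test with Fisher gives about 6%. A false difference is also not the main risk when the aim is to show that control is maintained.

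The textual conflict is softer than a flat contradiction. Section 3.3 keeps the threshold as its objective and still assesses rescue, and aim 2 puts the threshold at the same 30 minutes. What is missing is a hierarchy and a test. This stands, and it limits how strongly the point can be put.

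The tests compared are not the planned ones. Section 4 would use a mixed model for VAS. If its adverse-event rule were borrowed for the threshold, with Fisher only when an expected count is below 5, disagreement at 13 mm would be about 20% (16–23% for SD 20–30) at a better-arm mean of 45 mm. Need for rescue was not simulated.

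The exact-50 mm overlap would touch few patients, about 0.5–0.9 of 48 under these assumptions, or more if scores bunch at whole centimetres.

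Finally, naming either version would end the conflict. That is true, but the continuous one keeps more information, already has a model in section 4, and is on the scale of the 13 mm standard.

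**Conclusion.** The point holds in limited form. Sections 3 and 3.3 name different secondary outcomes, and section 4 gives no analysis for the binary one. The consequence depends on the truth: about 5% disagreement on significance if analgesia is equal, and about 16–35% if the arms differ by 13 mm (18–35% with Fisher, 16–28% with chi-square). At 13 mm, power is about 31–60% for the t-test and 14–34% for Fisher, so the binary version is the one likely to overlook a real loss of pain control.

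All these rates rest on assumed VAS means and SDs and on a single-time t-test. Baseline adjustment and the planned mixed model would change them. The definitional conflict and the 50 mm overlap rest on the text alone.

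**What to change.** In sections 1, 3, 3.3 and 4, name one secondary outcome: VAS in mm at 30 minutes. Estimate it from the planned mixed model with adjustment for time-0 VAS, and report the between-arm difference with a 95% CI read against the 13 mm the plan cites. The interval may be too wide to exclude 13 mm, but it will show that openly, whereas a non-significant test would not. List VAS ≤ 50 mm at 30 minutes and need for rescue as supportive outcomes, each with a named test.

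Separately, reconcile the adequate-control, rescue and entry passages, which currently all include a score of exactly 50 mm.

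The cost is wording only. VAS at 0 and 30 minutes is already scheduled, so no new data are needed. The price is that the threshold now in section 3, aim 2 and the hypothesis becomes supportive. The change should be made before the data are unblinded.

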A prospective study with 38 patients was conducted to describe the analgesic efficacy and side effect profile of low dose ketamine for acute severe pain in the emergency department (ED). The study trialed a bolus of ketamine (15mg) as intravenous push (IVP) followed by slow infusion (20mg) over 60 min. Patients were offered morphine 4mg as rescue analgesia at the 20-, 40-, and 60-minute marks. Pain was assessed on a 10-point verbal numerical reading scale (NRS), along with vital signs and sedation scores frequently over 120 minutes. At the 60-minute mark, side effect rating scale for dissociative anesthesia (SERSDA) scale was used to assess side effects. Twenty-two patients had clinically significant reduction in pain at 10 minutes. Twenty-five patients had clinically significant reduction at the end of the infusion (60 minutes). Twelve patients did not require or refused adjunct morphine therapy, as pain was adequately controlled throughout the duration of the study. There was a significant proportion of patients that experienced side effects (33 patients, 86%) with a large portion grading them as weak or modest (20 patients, 53%). Thirteen patients (34%) reported side effects as “very bothersome”. The most common side effects were dizziness, fatigue, nausea and feeling of unreality. A large portion of patients (32 patients, 84%) reported they would trial ketamine again for pain management.⁷

A case series looked at 14 patients in an urban ED who received low dose ketamine (0.2-0.4mg/kg) infusions (10-15min) for analgesia. Thirteen patients had received analgesia prior to the ketamine infusion. No patient received rescue analgesia one hour post

infusion. There were no dangerous adverse effects noted. One patient reported tinnitus and uneasiness during the infusion while another reported dizziness.⁸

A recent study conducted in 2017 aimed to show reduction in side effects of LDK by giving it over 15 minutes compared to standard IVP of less than 5 minutes. A total of 48 patients were enrolled and the study showed similar rates of side effects except for overall feeling of unreality, which was significantly higher in IVP group (91.7% vs 54.2%, $p=0.008$). There were similar decreases in pain scores for each group ($p=0.14$) with no significant difference in use of rescue analgesia or change in vital signs.²

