Data from this double-blind, double dummy, randomized comparative study will be imported into SPSSv25.0 software (IBM Corp., Armonk, NY) with baseline characteristics summarized by treatment arm. A generalized linear model using an underlying gamma distribution will be employed for all ordinal data including SERDSA outcomes collected at time points before complete resolution to "0". A mixed model regression will be employed for all continuous outcomes across time with missing data assumed to be random. Boxplots of outcome will also be provided at each study time point stratified by study arm. Additionally, the rates of adverse events will be summarized using frequencies and percentages and compared between study arms via Fisher's exact or Pearson chi-square tests depending on cell sample size distribution.

Variables collected during the study include patient demographics (age, sex, pain type/location), vital signs on presentation as well as during specified times (heart rate, blood pressure, respiratory rate, and oxygen saturation), Visual Analogue Scale (VAS) scores, SERSDA scores¹⁷, Richmond Agitation-Sedation Scale (RASS) and time to rescue analgesia.

If patients withdraw from the study prior to medication administration, they will not be included in the final data set. If they decide to withdraw while medication is being administered or after the completion of the infusion, but during the follow-up period of 90 minutes, they will be in the final data set and shown on the diagram as withdrawn.

There may be CITI trained and CRC Credentialed medical students, ED residents and faculty members who will help with the enrollment process and data collection.

Data for this study will be collected in REDCap. REDCap is a HIPAA compliant clinical electronic data capture system. All patient records entered into REDCap will have identifiers removed and will be given a unique study-specific code. Patient identifiers (patient name, DOB, MRN) with codes will be stored separately in an Excel spreadsheet located in a secure folder on the Summa G:/ drive, accessible only to authorized study personnel. Only authorized study personnel will be given access to the data collection sheet in REDCap. Multi-factor authentication (MFA) security is used to access the

Ketamine 30 min vs 15 min

Version: 7

Date: 06.06.2024

Page 12 of 15

REDCap platform. Full audit trails are kept within REDCap.

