APPENDIX A

Visual Analogue Scale (VAS)

Side Effects Rating Scale for Dissociative Anesthetics (SERSDA) Scale

Side Effects	Severity	Scale
Fatigue		0, No Change
Dizziness		1, Weak
Headache		2, Modest
Feeling of Unreality		3, Bothersome
Change in Hearing		4, Very Bothersome
Change in Vision		
Mood Change		
Generalized Discomfort		
Hallucination		

The Richmond Agitation Sedation Scale (RASS)

+4	Combative	violent, immediate danger to staff
+3	Very Agitated	Pulls or removes tube(s) or catheter(s); aggressive
+2	Agitated	Frequent non-purposeful movement, fights ventilator
+1	Restless	Anxious, apprehensive but movements not aggressive or vigorous
0	Alert & calm	
-1	Drowsy	Not fully alert, but has sustained awakening to voice (eye opening & contact \geq 10 sec)
-2	Light sedation	Briefly awakens to voice (eye opening & contact < 10 sec)
-3	Moderate sedation	Movement or eye-opening to voice (but no eye contact)
-4	Deep sedation	No response to voice, but movement or eye opening to physical stimulation
-5	Unarousable	No response to voice or physical stimulation

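### The gamma model set for all ordinal data cannot take RASS as scored (six of its ten levels are 0 or negative), so the trial's only sedation scale has no workable comparison between arms

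*Combined protocol and SAP*

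**What the plan says.** Section 4 (Data Analysis/Plan) gives one rule for ordinal outcomes: "A generalized linear model using an underlying gamma distribution will be employed for all ordinal data". The same section's list of collected variables includes "Richmond Agitation-Sedation Scale (RASS) and time to rescue analgesia". Section 3.3 gives the scale's role: "The Richmond Agitation Sedation Scale (RASS) (Appendix A) will be used to collect additional data". The Study Schedule in that section places RASS at 5, 30 and 90 minutes.

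Appendix A sets out ten RASS levels. Agitation runs from +1 to +4, alert and calm is 0, and sedation runs from -1 to -5. The mildest sedation level, -1, is described as "Not fully alert, but has sustained awakening to voice".

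Section 4 has four other provisions that might bear on RASS:

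- A mixed model, for continuous outcomes only.
- Graphs: "Boxplots of outcome will also be provided at each study time point stratified by study arm".
- Adverse events: "the rates of adverse events will be summarized using frequencies and percentages", compared between arms by Fisher's exact or chi-square test.
- A remark on scores of 0, attached to SERSDA, which limits that analysis to time points before the score has returned to 0.

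**The concern.** RASS is an ordered category scale, so the rule for ordinal data covers it although the sentence does not name it. The model chosen is defined only for positive values, and most of the RASS scale is not positive. If the rule is followed to the letter, the ratings that describe sedation are the ones that cannot be analysed.

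The stake is limited but real. The trial asks whether a slower infusion is better tolerated, and RASS is its only sedation scale; SERSDA has a fatigue item but none for sedation. The documents do not show whether sedation differs between 15 and 30 minutes. The remark on sedation in section 1 concerns IV push against a slower infusion, and section 2 says of that trial that "the study showed similar rates of side effects except for overall feeling of unreality". The RASS ratings here would be the trial's own evidence on the point, and the stated model cannot use them.

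**Working it through.** **Inputs.** Gamma model for ordinal data and 24 subjects per arm (section 4); RASS levels +4 to -5 (Appendix A); ratings at 5, 30 and 90 minutes (section 3.3). The documents give no RASS frequencies, so every rate below is an assumption.

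**The plan's own figure.** The plan states no number for RASS. Its one calculated number is the sample size for SERSDA: difference 1, SD 1.2, two-sided 5%, power 80%. The normal formula gives 2 × (1.960 + 0.842)² × 1.2² / 1² = 22.6, or 23 per arm. The t-test version gives 23.6, or 24 per arm, with power 80.7% at 24. The stated 24 per arm reproduces and serves here only as the denominator.

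**Step 1: which levels the model accepts.** The gamma likelihood contains log(y), which is undefined for negative y and unbounded at 0. The log-density was evaluated at each level with shape 2 and scale 1:

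| RASS | Meaning | Levels | Gamma log-density |
|---|---|---|---|
| +1 to +4 | agitation | 4 | finite (-1.00, -1.31, -1.90, -2.61) |
| 0 | alert and calm | 1 | minus infinity |
| -1 to -5 | sedation | 5 | minus infinity |

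Levels outside the model: 1 + 5 = 6 of 10, including every sedation level. This step needs no assumption about rates.

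**Step 2: does a fit run anyway?** A gamma model with log link was fitted to 48 simulated ratings, 24 per arm, under three assumed distributions:

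| Assumed distribution | Expected ratings above 0 | Result on RASS as scored |
|---|---|---|
| 70% at 0, 25% at -1, 5% at -2 | 48 × 0 = 0 | stopped, estimation infeasible |
| 70% at 0, 20% at -1, 5% at -2, 5% at +1 | 48 × 0.05 = 2.4 | stopped, estimation infeasible |
| 50% at 0, 20% at -1, 10% at -2, 15% at +1, 5% at +2 | 48 × 0.20 = 9.6 | standard errors above 1 million, log-likelihood undefined |

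**Step 3: what remains if the inadmissible ratings are dropped.** With 5% agitated, 48 × 0.05 = 2.4 ratings remain at a time point; with 10%, 48 × 0.10 = 4.8. None comes from a sedated subject. The chance that both arms have at least one usable rating is (1 - 0.95²⁴)² = 0.50 or (1 - 0.90²⁴)² = 0.85.

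**Step 4: what a count of sedated subjects would offer.** Exact two-sided Fisher power at 5%, 24 per arm, for RASS -1 or lower:

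| Assumed sedated, arm vs arm | Power |
|---|---|
| 20% vs 10% | 10% |
| 30% vs 10% | 31% |
| 40% vs 10% | 60% |
| 50% vs 10% | 83% |

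For scale, p = 0.0496 at 5 vs 0 of 24 and p = 0.036 at 9 vs 2 of 24.

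**Step 5: whether another provision fills the gap.** The mixed model is for continuous outcomes. Boxplots display data but do not compare arms, and RASS is not named for them. The adverse-event tests could include sedation only if some RASS level counted as an event, and none is defined. The remark on 0 is tied to SERSDA, where 0 means the effect is absent; it says nothing about negative scores.

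**The case against.** The strongest reply is that this is a gap in wording that one coding decision closes. Adding 6 to every RASS score gives a range of 1 to 10, and the gamma model then fitted in all three assumed data sets. That is true, but the plan states no shift. The constant is arbitrary, the ratio estimated under a log link depends on it, and the choice would be made after data exist. A shifted score also puts sedation and agitation on one line, so more of each in the same arm can cancel.

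A second reply is that little depends on RASS. It is not a named outcome, sedation is not among the side effects listed for monitoring in section 3.3, and no threshold or power statement uses it. This stands, and it limits the weight of the point.

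Third, the proposed replacement has low power for modest differences, and the RASS schedule has limits that no analysis removes. There is no rating at 0 or 15 minutes. At 30 minutes one arm is just finishing ketamine while the other finished 15 minutes before. By 90 minutes some subjects may have received rescue fentanyl. These limits also stand. They are reasons to call the comparisons exploratory and to interpret them with care, not reasons to keep a model that cannot run.

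Fourth, a proportional-odds model or a rank test would take RASS as scored. Either is valid. Counts in each direction are preferred here because they keep sedation and agitation apart and use a test already in the plan. The same gamma sentence also governs SERSDA; this point covers only RASS, whose negative codes and two opposite directions need their own analysis.

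**Conclusion.** The concern holds. This is a stated rule that fails when it is followed, and nothing else in the plan supplies a RASS comparison. The core of the conclusion, six of ten levels outside the gamma range and every sedation level among them, rests only on section 4 and Appendix A. The counts of usable ratings and the power figures rest on assumed rates and show scale only.

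The consequence is moderate: the plan should be corrected, but the main conclusions of the trial do not turn on this point.

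**What to change.** In section 4, state that RASS is not analysed with the gamma model. At 5, 30 and 90 minutes, report by arm the number and percentage of rated subjects with RASS -1 or lower and, separately, with RASS +1 or higher. Compare arms with Fisher's exact test, and label the 2 × 3 = 6 comparisons exploratory.

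The cost is one or two sentences of analysis text. The ratings are already scheduled and the test is already in the plan, so no further subjects, visits or staff are needed. The gain is a valid count and comparison by arm; it does not give the trial good power to detect a modest difference in sedation.
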